7.5 Vital Signs (Blood Pressure, Pulse Rate, Respiration Rate, and Temperature)

Vital signs will be performed at the following time points:

Table 7.5 Vital Signs Time Points

Day	Time Point	Parameter
Screening		HR, BP, RR, T
Day -1	Check-in	HR, BP, RR, T
Day 1	Predose	HR, BP, RR, T
Day 1	Hour 2 , Hour 4	HR, BP, RR
Day 2		HR, BP, RR
Day 3		HR, BP, RR
Day 4		HR, BP, RR
Day 5		HR, BP, RR
Day 6		HR, BP, RR
Day 7		HR, BP, RR
Day 8	EOT or ET*	HR, BP, RR, T

*performed at EOT or prior to ET

Descriptive statistics will be reported for vital sign measurements (blood pressure [BP], pulse [HR], and respiration rate [RR]) and change from baseline by cohort and time point. Baseline is the last non-missing predose measurement prior to dosing (Day 1 Predose), including unscheduled assessments. Postdose unscheduled values and ET results will not be used for calculation of descriptive statistics. All vital signs results will be listed by subject.

7.6 ECG (Heart Rate, PR, QRS, QT, and QTcF [QT with Fridericia correction])

Single 12-lead ECGs will be performed at the following time points:

Table 7.6: ECG Time Points

Day
Screening
Day -1
Day 8*
* performed at EOT or prior to ET

Descriptive statistics will be reported for ECG parameters and change from baseline by cohort and time point. Baseline is the last non-missing predose measurement prior to dosing (Day -1), including unscheduled assessments. Postdose unscheduled values and ET results will not be used for calculation of descriptive statistics. All ECG interval parameters will be listed by subject and time point of collection with QTcF > 450 msec and change from baseline > 30 msec flagged.

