14.2.3 ECG Monitoring

Single 12-lead ECGs will be performed as outlined in the Study Events Flow Chart (Section 7). Additional ECGs may be taken at any other times, if deemed necessary by the PI or designee.

ECGs will be performed with subjects in a supine position (at least 10 minutes). All ECG tracings will be reviewed by the PI or designee.

ECGs will be measured at Screening, at Check-in (Day -1), and at the EOT or ET (CRU discharge). ECGs will be obtained prior to and as close as possible to the scheduled blood draws if scheduled at the same time.

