15.3.2 Safety Analyses

All safety data will be populated in the individual CRFs. All safety data will be listed by subjects.

Dosing dates and times will be listed by subject.

AEs will be coded using the Medical Dictionary for Regulatory Activities (MedDRA[®]) and summarized by treatment for the number of subjects reporting the TEAE. A by-subject AE data listing including verbatim term, coded term, treatment, severity, and relationship to treatment will be provided.

Safety data including ECGs, physical examinations, vital signs assessments, clinical laboratory results, will be summarized by treatment and point of time of collection.

Descriptive statistics using appropriate summary statistics will be calculated for quantitative safety data as well as for the difference to baseline, when appropriate.

Concomitant medications will be listed by subject and coded using the World Health Organization drug dictionary. Medical history will be listed by subject.

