7. SAFETY

No inferential statistics are to be performed for the safety analysis.

All clinical safety and tolerability data will be listed by cohort, subject and assessment time points, chronologically. This will include unscheduled assessments (including rechecks) and ET records.

Continuous variables will be summarized using n, mean, SD, minimum, median, and maximum. Frequency counts will be reported for categorical data when appropriate. The level of precision will be presented as follows: “n” as an integer, minimum/maximum in same precision as in the database, mean/median in one more precision level than minimum/maximum, and SD in one more precision level than mean/median. Where individual data points are missing because of dropouts or other reasons, the data will be summarized based on reduced denominators.

When change from baseline is calculated, baseline is the last scheduled or unscheduled assessment before dosing on Day 1, whichever is later. Unscheduled assessments and ET measurements taken after dosing will not be used in the summarization.

Note: The term ‘unscheduled’ assessment used in this SAP may also refer to recheck assessments.

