7.4 Clinical Laboratory Tests (Serum Chemistry, Hematology, Coagulation, and Urinalysis)

All clinical laboratory test results will be presented in by-subject data listings, however, only serum chemistry, hematology, coagulation and urinalysis values will be summarized. Given that this study was conducted at multiple sites, by-subject data listings will be provided in conventional units and international system of units (SI units). Summary tables will be provided in SI units.

Hematology, coagulation, serum chemistry and urinalysis tests will be conducted at the following time points:

Table 7.4 Lab Test Time Points

Day
Screening*
Day -1*
Day 2
Day 5
Day 8**

* performed following a fast of at least 12 hours
** performed at EOT or prior to ET

Out-of-normal range flags will be presented in the clinical laboratory listings as recorded in the database. The reference ranges used during the study will be provided in conventional and SI units by study site in Appendix 16.1.10.1. Out-of-range values and unscheduled results will be listed. Results that are indicated as CS by the PI (either in the PI flag or in PI comments) will be listed in the table.

For all laboratory values that are numeric, descriptive statistics (n, mean, SD, minimum, median, and maximum) will be presented for each laboratory test by cohort and time point. Change from baseline will also be summarized. Postdose unscheduled assessments and ET results will not be summarized.

For each laboratory test, a shift table will be developed comparing the frequency of the results at baseline (above normal, normal, or below normal) to postdose results. For urinalysis tests, the categories are normal and outside normal.

Baseline is the last non-missing predose measurement prior to dosing (Day -1), including unscheduled assessments.

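### The SAP leaves early-termination ECGs out of the ECG summaries, so the only scheduled postdose ECG of a subject withdrawn before Day 8 is never summarised

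*SAP*

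**What the plan says.** The schedule comes from the protocol. Section 14.2.3 states: "ECGs will be measured at Screening, at Check-in (Day -1), and at the EOT or ET (CRU discharge". That is two predose ECGs and one postdose ECG per subject. SAP Table 7.6 repeats this: Screening, Day -1 and Day 8, with Day 8 footnoted as "performed at EOT or prior to ET".

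The exclusion comes from the SAP. Section 7 sets a general rule: "Unscheduled assessments and ET measurements taken after dosing will not be used in the summarization". Section 7.6 applies it to ECG: "Postdose unscheduled values and ET results will not be used for calculation of descriptive statistics". Section 7.4 does the same for laboratory tests: "Postdose unscheduled assessments and ET results will not be summarized". Section 7.5 uses the ECG wording for vital signs.

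Two further statements set the context. Protocol 15.3.2 promises: "Safety data including ECGs, physical examinations, vital signs assessments, clinical laboratory results, will be summarized by treatment and point of time of collection". SAP 7 says how gaps are handled: "Where individual data points are missing because of dropouts or other reasons, the data will be summarized based on reduced denominators".

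**The concern.** The ET ECG is not an extra reading. For a subject who leaves early, it is the scheduled postdose ECG. Table 7.6 treats it as the Day 8 assessment, and the sentence that follows keeps it out of the descriptive statistics. Tables 14.3.5.12 and 14.3.5.13 are labelled Safety Population, which SAP 4.1 defines as all dosed subjects, but their postdose rows describe only those who reached Day 8.

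Safety and tolerability in renal impairment is a secondary objective, and the cohorts are small. Adverse events are among the reasons for withdrawal in Protocol 12.3, so an omitted ECG could come from a subject of particular interest. ECG also has no second route into a Section 14 data table. The SAP plans no ECG outlier or abnormality table, and the flags for QTcF above 450 msec and for a rise of more than 30 msec appear only in the listing.

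**Working it through.** There is no planned figure to reproduce. The check is a count of the scheduled postdose time points that stay in the summaries.

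**Inputs**
- ECG (SAP Table 7.6): Day 8 only, so 1 postdose time point.
- Laboratory tests (SAP Table 7.4): Days 2, 5 and 8, so 3.
- Heart rate, blood pressure and respiration (SAP Table 7.5): Day 1 Hours 2 and 4, then Days 2 to 8, so 2 + 7 = 9.
- In each table, only Day 8 is marked as EOT or ET.
- Renal-impairment cohort size (SAP 3): up to 8. Healthy controls (SAP Table 5.1): 8 up to 24.

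**Rule applied.** The measurement on the day of withdrawal is taken to be the ET record and is excluded. Scheduled values before that day are kept, because the tables are laid out by cohort and time point. For laboratory tests, SAP 7.4 says "descriptive statistics (n, mean, SD, minimum, median, and maximum) will be presented for each laboratory test by cohort and time point".

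| Withdrawn on | ECG kept | Laboratory kept | Vital signs kept |
|---|---|---|---|
| Day 1, after Hour 4 | 0 of 1 | 0 of 3 | 2 of 9 |
| Day 3 | 0 of 1 | 1 of 3 | 3 of 9 |
| Day 6 | 0 of 1 | 2 of 3 | 6 of 9 |
| Day 7 | 0 of 1 | 2 of 3 | 7 of 9 |

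The ECG column is zero for every withdrawal before Day 8. An unscheduled ECG taken earlier after dosing would not help, since the same sentences exclude those too. In Table 14.3.5.12 the subject remains in the Screening and Day -1 rows. Table 14.3.5.13 drops those rows, so there the subject is absent altogether.

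A subject is missing from the postdose laboratory summaries only if withdrawn before a scheduled Day 2 sample, and from the vital-sign summaries only if withdrawn before Hour 2. Temperature also has its only scheduled postdose value at Day 8 or ET, but SAP 7.5 does not name it among the parameters to be summarised.

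**Size per withdrawal**
- Renal-impairment cohort of 8: 1/8 = 12.5% of the postdose ECG summary.
- Healthy controls: from 1/8 = 12.5% with 8 subjects down to 1/24 = 4.2% with 24.

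**Number of withdrawals.** Not given. The outputs bound with the SAP show 7 pairs in the severe comparison and 33 observations in the ANCOVA, but these do not show that anyone left after dosing. Enrolment was up to 8 per cohort, and PK evaluability and the availability of a match also affect those counts.

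**The case against.** There are several good points in favour of the SAP as written.

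- **The exclusion removes a record, not a subject.** A reader might infer that withdrawn subjects disappear from the postdose safety tables. They do not: earlier scheduled laboratory and vital-sign values stay in with reduced denominators, and the adverse-event tables use the number dosed. This stands, and it confines the point to ECG.
- **ET laboratory values are not confined to listings.** The shell for the out-of-range tables (14.3.4.1 to 14.3.4.3) sorts early-termination records in with the scheduled ones, and Table 14.3.4.4 shows all time points for a test with a clinically significant value. This stands, and ECG has no counterpart.
- **No count of subjects with a QTcF rise is distorted.** A reader might picture 0 of 7 reported in place of 1 of 8. No categorical QTcF table is planned, so the effect is on n, mean, SD, minimum, median and maximum.
- **Serious findings are still captured.** Under Protocol 14.2.6.2, ECG abnormalities that the investigator judges clinically significant are handled as adverse events. This stands for those findings. A change not judged significant would still be seen only in the listing.
- **No clear departure from the protocol.** Protocol 15.3.2 speaks of summaries by time of collection, and an ET visit has no fixed nominal time. The synopsis qualifies the promise with where possible, and Protocol 15.3 leaves detailed methods to the SAP. The silence of SAP Section 8 is therefore not shown to be an error.
- **Pooling mixes exposures.** With a half-life of about 24 hours, Day 8 lies 168/24 = 7 half-lives after the dose, whereas an ET ECG on Day 2 or 3 is taken at much higher exposure. This is a fair reason to leave the nominal Day 8 row alone. It is not a reason to leave the earlier ECG out of every summary.

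**Conclusion.** The point holds for ECG. By an explicit rule, the postdose content of Tables 14.3.5.12 and 14.3.5.13 is limited to subjects who reach Day 8, and the ET ECG survives only in Appendix 16.2.8.3. Each withdrawal after dosing and before Day 8 costs 12.5% of the postdose ECG summary in a renal-impairment cohort of 8.

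This assumes that the exclusion sentence overrides the EOT-or-ET footnote, so that an ET ECG is not filed and summarised as Day 8. The exclusion is stated in both SAP 7 and SAP 7.6, so that is the natural reading.

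The documents do not support a finding that the ECG results are biased. The number of withdrawals and their reasons are not given, and the place of adverse events at the head of the list in Protocol 12.3 says nothing about frequency. This is a low-cost improvement to the safety reporting.

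**What to change.** In SAP 7 and 7.6, allow ET ECG results to be summarised. Add one row, 'EOT/ET (last postdose value)', to Tables 14.3.5.12 and 14.3.5.13. It takes the Day 8 value for completers and the ET value for subjects who left early; other unscheduled ECGs stay out. Keep the nominal Day 8 row, and footnote that the new row combines Day 8 with earlier times.

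The same row in the laboratory shift tables (14.3.5.3, 14.3.5.6 and 14.3.5.9) is optional, since those tables already carry the scheduled values before withdrawal.

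The cost is a wording change and one row in each of two tables, from data already collected. The downside is the mixed timing in that row. Because the SAP file already contains outputs dated 30 April 2020, the change may have to be recorded in the clinical study report, as the SAP Introduction provides. If nobody left between dosing and Day 8, one sentence in the report saying so is enough.

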7.7 Concomitant Medications

All concomitant medications recorded during the study will be coded with the WHO Dictionary, Version 01Sep2018 B3 and listed.

7.8 Physical Examination

A full physical examination will be performed at Screening and on Day 8 or upon ET. Abbreviated physical examinations will be performed at Check-in (Day -1) and 1 hour postdose. Symptom-driven physical examinations may be performed at other times, at the PI's or designee's discretion. Abnormal findings will be reported as medical history or adverse events by the clinical site. Physical examination results will be listed by subject and time point.

8. SUMMARY OF CHANGES FROM PROTOCOL-PLANNED ANALYSIS

Paired t-tests to evaluate the effect of renal function group were added in the analysis plan.

The rest of the analyses described in this SAP are aligned with those analyses described in the protocol.

9. SUMMARY TABLES AND FIGURES

Summary tables and figures are numbered following the International Conference on Harmonization (ICH) structure but may be renumbered as appropriate during the compilation of the tables and figures for the CSR. Note that all summary tables and figures will be generated using SAS® Version 9.3 or higher.

9.1 In-text Summary Tables and Figures

The following is a list of table and figure titles that will be included in the text of the CSR. Tables and figures will be numbered appropriately during compilation of the CSR.

Section 10:

Table 10-1 Summary of Disposition (Safety Population)

Section 11:

Table 11-1 Demographic Summary (Safety Population)

Total Plasma LOXO-292

Table 11-2 Summary of Total Plasma LOXO-292 Pharmacokinetic Parameters Following Administration of a Single Dose of 160 mg LOXO-292 to

Subjects with Mild, Moderate, and Severe Renal Impairment and to Healthy Matched Control Subjects (Pharmacokinetic Population)

Table 11-3 Summary of Statistical Comparisons of Total Plasma LOXO-292 Pharmacokinetic Parameters Following Administration of a Single Dose of 160 mg LOXO-292 to Subjects with Mild Renal Impairment Versus Healthy Matched Control Subjects (Paired T-Test) (Pharmacokinetic Population)

Table 11-4 Summary of Statistical Comparisons of Total Plasma LOXO-292 Pharmacokinetic Parameters Following Administration of a Single Dose of 160 mg LOXO-292 to Subjects with Moderate Renal Impairment Versus Healthy Matched Control Subjects (Paired T-Test) (Pharmacokinetic Population)

Table 11-5 Summary of Statistical Comparisons of Total Plasma LOXO-292 Pharmacokinetic Parameters Following Administration of a Single Dose of 160 mg LOXO-292 to Subjects with Severe Renal Impairment Versus Healthy Matched Control Subjects (Paired T-Test) (Pharmacokinetic Population)

Table 11-6 Summary of Statistical Comparisons of Total Plasma LOXO-292 Pharmacokinetic Parameters Following Administration of a Single Dose of 160 mg LOXO-292 to Subjects with Mild Renal Impairment Versus Healthy Matched Control Subjects (Pharmacokinetic Population)

Table 11-7 Summary of Statistical Comparisons of Total Plasma LOXO-292 Pharmacokinetic Parameters Following Administration of a Single Dose of 160 mg LOXO-292 to Subjects with Moderate Renal Impairment Versus Healthy Matched Control Subjects (Pharmacokinetic Population)

Table 11-8 Summary of Statistical Comparisons of Total Plasma LOXO-292 Pharmacokinetic Parameters Following Administration of a Single Dose of 160 mg LOXO-292 to Subjects with Severe Renal Impairment Versus Healthy Matched Control Subjects (Pharmacokinetic Population)

Figure 11-1 Arithmetic Mean Total Plasma LOXO-292 Concentration-Time Profiles Following Administration of a Single Dose of 160 mg LOXO-292 to Subjects with Mild, Moderate, and Severe Renal Impairment and to Healthy Matched Control Subjects (Pharmacokinetic Population)

Figure 11-2 Individual Total Plasma LOXO-292 AUC_{0-t} Values, Geometric Means With Corresponding 95% CIs, and GMR With Corresponding 90% CIs Following Administration of a Single Dose of 160 mg LOXO-292 to Subjects with Mild, Moderate, and Severe Renal Impairment and to Healthy Matched Control Subjects (Pharmacokinetic Population)

Figure 11-3 Individual Total Plasma LOXO-292 AUC_{0-inf} Values, Geometric Means With Corresponding 95% CIs, and GMR With Corresponding 90% CIs Following Administration of a Single Dose of 160 mg LOXO-292 to Subjects with Mild, Moderate, and Severe Renal Impairment and to Healthy Matched Control Subjects (Pharmacokinetic Population)

Figure 11-4 Individual Total Plasma LOXO-292 C_{max} Values, Geometric Means With Corresponding 95% CIs, and GMR With Corresponding 90% CIs Following Administration of a Single Dose of 160 mg LOXO-292 to Subjects with Mild, Moderate, and Severe Renal Impairment and to Healthy Matched Control Subjects (Pharmacokinetic Population)

Unbound Plasma LOXO-292

Table 11-9 Summary of Unbound Plasma LOXO-292 Pharmacokinetic Parameters Following Administration of a Single Dose of 160 mg LOXO-292 to Subjects with Mild, Moderate, and Severe Renal Impairment and to Healthy Matched Control Subjects (Pharmacokinetic Population)

Table 11-10 Summary of Statistical Comparisons of Unbound Plasma LOXO-292 Pharmacokinetic Parameters Following Administration of a Single Dose of 160 mg LOXO-292 to Subjects with Mild Renal Impairment Versus Healthy Matched Control Subjects (Paired T-Test) (Pharmacokinetic Population)

Table 11-11 Summary of Statistical Comparisons of Unbound Plasma LOXO-292 Pharmacokinetic Parameters Following Administration of a Single Dose of 160 mg LOXO-292 to Subjects with Moderate Renal Impairment Versus Healthy Matched Control Subjects (Paired T-Test) (Pharmacokinetic Population)

Table 11-12 Summary of Statistical Comparisons of Unbound Plasma LOXO-292 Pharmacokinetic Parameters Following Administration of a Single Dose of 160 mg LOXO-292 to Subjects with Severe Renal Impairment Versus Healthy Matched Control Subjects (Paired T-Test) (Pharmacokinetic Population)

Table 11-13 Summary of Statistical Comparisons of Unbound Plasma LOXO-292 Pharmacokinetic Parameters Following Administration of a Single Dose of 160 mg LOXO-292 to Subjects with Mild Renal Impairment Versus Healthy Matched Control Subjects (Pharmacokinetic Population)

Table 11-14 Summary of Statistical Comparisons of Unbound Plasma LOXO-292 Pharmacokinetic Parameters Following Administration of a Single Dose of 160 mg LOXO-292 to Subjects with Moderate Renal Impairment Versus Healthy Matched Control Subjects (Pharmacokinetic Population)

Table 11-15 Summary of Statistical Comparisons of Unbound Plasma LOXO-292 Pharmacokinetic Parameters Following Administration of a Single Dose of 160 mg LOXO-292 to Subjects with Severe Renal Impairment Versus Healthy Matched Control Subjects (Pharmacokinetic Population)

Figure 11-5 Arithmetic Mean Unbound Plasma LOXO-292 Concentration-Time Profiles Following Administration of a Single Dose of 160 mg LOXO-292 to Subjects with Mild, Moderate, and Severe Renal Impairment and to Healthy Matched Control Subjects (Pharmacokinetic Population)

Figure 11-6 Individual Unbound Plasma LOXO-292 AUC_{0-t,u} Values, Geometric Means With Corresponding 95% CIs, and GMR With Corresponding 90% CIs Following Administration of a Single Dose of 160 mg LOXO-292 to Subjects with Mild, Moderate, and Severe Renal Impairment and to Healthy Matched Control Subjects (Pharmacokinetic Population)

Figure 11-7 Individual Unbound Plasma LOXO-292 AUC_{0-inf,u} Values, Geometric Means With Corresponding 95% CIs, and GMR With Corresponding 90% CIs Following Administration of a Single Dose of 160 mg LOXO-292 to Subjects with Mild, Moderate, and Severe Renal Impairment and to Healthy Matched Control Subjects (Pharmacokinetic Population)

Figure 11-8 Individual Unbound Plasma LOXO-292 C_{max,u} Values, Geometric Means With Corresponding 95% CIs, and GMR With Corresponding 90% CIs Following Administration of a Single Dose of 160 mg LOXO-292 to Subjects with Mild, Moderate, and Severe Renal Impairment and to Healthy Matched Control Subjects (Pharmacokinetic Population)

Urine LOXO-292

Table 11-16 Summary of Urine LOXO-292 Pharmacokinetic Parameters Following Administration of a Single Dose of 160 mg LOXO-292 to Subjects with Mild, Moderate, and Severe Renal Impairment and to Healthy Matched Control Subjects (Pharmacokinetic Population)

Figure 11-9 Arithmetic Mean Cumulative % Dose of LOXO-292 Excreted Unchanged in Urine Following Administration of a Single Dose of 160 mg LOXO-292 to Subjects with Mild, Moderate, and Severe Renal Impairment and to Healthy Matched Control Subjects (Pharmacokinetic Population)

Section 12:

Table 12-1 Treatment-Emergent Adverse Event Frequency by Cohort – Number of Subjects Reporting the Event (% of Subjects Dosed) (Safety Population)

9.2 Section 14 Summary Tables and Figures

The following is a list of table and figure titles that will be included in Section 14 of the report. Table and figure titles may be renumbered as appropriate during the compilation of the report.

14.1 Demographic Data Summary Tables

14.1.1 Demographic Tables

Table 14.1.1.1 Summary of Disposition (Safety Population)

Table 14.1.1.2 Demographic Summary (Safety Population)

14.2 Pharmacokinetic Data Summary Tables and Figures

14.2.1 Total Plasma LOXO-292 Tables

Table 14.2.1.1 Total Plasma LOXO-292 Concentrations (ng/mL) Following Administration of a Single Dose of 160 mg LOXO-292 to Subjects with Mild Renal Impairment (Pharmacokinetic Population)

Table 14.2.1.2 Total Plasma LOXO-292 Concentrations (ng/mL) Following Administration of a Single Dose of 160 mg LOXO-292 to Subjects with Moderate Renal Impairment (Pharmacokinetic Population)

Table 14.2.1.3	Total Plasma LOXO-292 Concentrations (ng/mL) Following Administration of a Single Dose of 160 mg LOXO-292 to Subjects with Severe Renal Impairment (Pharmacokinetic Population)
Table 14.2.1.4	Total Plasma LOXO-292 Concentrations (ng/mL) Following Administration of a Single Dose of 160 mg LOXO-292 to Healthy Matched Control Subjects (Pharmacokinetic Population)
Table 14.2.1.5	Total Plasma LOXO-292 Pharmacokinetic Parameters Following Administration of a Single Dose of 160 mg LOXO-292 to Subjects with Mild Renal Impairment (Pharmacokinetic Population)
Table 14.2.1.6	Total Plasma LOXO-292 Pharmacokinetic Parameters Following Administration of a Single Dose of 160 mg LOXO-292 to Subjects with Moderate Renal Impairment (Pharmacokinetic Population)
Table 14.2.1.7	Total Plasma LOXO-292 Pharmacokinetic Parameters Following Administration of a Single Dose of 160 mg LOXO-292 to Subjects with Severe Renal Impairment (Pharmacokinetic Population)
Table 14.2.1.8	Total Plasma LOXO-292 Pharmacokinetic Parameters Following Administration of a Single Dose of 160 mg LOXO-292 to Healthy Matched Control Subjects (Pharmacokinetic Population)
Table 14.2.1.9	Intervals (Hours) Used for Determination of Total Plasma LOXO-292 Kel Values Following Administration of a Single Dose of 160 mg LOXO-292 to Subjects with Mild, Moderate, and Severe Renal Impairment and to Healthy Matched Control Subjects (Pharmacokinetic Population)
Table 14.2.1.10	Statistical Comparisons of Total Plasma LOXO-292 Pharmacokinetic Parameters Following Administration of a Single Dose of 160 mg LOXO 292 to Subjects with Mild Renal Impairment Versus Healthy Matched Control Subjects (Paired T-Test) (Pharmacokinetic Population)
Table 14.2.1.11	Statistical Comparisons of Total Plasma LOXO-292 Pharmacokinetic Parameters Following Administration of a Single Dose of 160 mg LOXO 292 to Subjects with Moderate Renal Impairment Versus Healthy Matched

Control Subjects (Paired T-Test) (Pharmacokinetic Population)

Table 14.2.1.12 Statistical Comparisons of Total Plasma LOXO-292 Pharmacokinetic Parameters Following Administration of a Single Dose of 160 mg LOXO 292 to Subjects with Severe Renal Impairment Versus Healthy Matched Control Subjects (Paired T-Test) (Pharmacokinetic Population)

Table 14.2.1.13 Statistical Comparisons of Total Plasma LOXO-292 Pharmacokinetic Parameters Following Administration of a Single Dose of 160 mg LOXO 292 to Subjects with Mild Renal Impairment Versus Healthy Matched Control Subjects (Pharmacokinetic Population)

Table 14.2.1.14 Statistical Comparisons of Total Plasma LOXO-292 Pharmacokinetic Parameters Following Administration of a Single Dose of 160 mg LOXO 292 to Subjects with Moderate Renal Impairment Versus Healthy Matched Control Subjects (Pharmacokinetic Population)

Table 14.2.1.15 Statistical Comparisons of Total Plasma LOXO-292 Pharmacokinetic Parameters Following Administration of a Single Dose of 160 mg LOXO 292 to Subjects with Severe Renal Impairment Versus Healthy Matched Control Subjects (Pharmacokinetic Population)

